12.1. Ravidasvir Pharmacokinetic (PK) assessments

12.1.1. Intensive PK study

In stage 1, in selected centres, intensive PK sampling: 0 (pre-dose), 1, 2, 3, 4, 6, 8 and 24 hours' post-dose at Week 4 will be performed in 25 HCV mono-infected patients receiving ravidasvir 200 mg, once daily in the morning. The steady-state pharmacokinetic parameters of ravidasvir, AUC₀₋₂₄, Cmax, Tmax, Cmin, predose (C0), C24, apparent oral clearance (CL/F) and apparent volume of distribution (Vd/F) will be determined using a non-compartmental analysis. Subjects will be asked to fast at least 6 hours prior to the intensive PK sampling visit and until 2 hours after dosing at site.

12.1.2. Sparse PK samples collection

In both stage 1 and stage 2, population PK parameters using sparse sampling is estimated on other subjects using non-linear mixed effects regression. Exact timing of drug intake as well as relationship with food intake is recorded for all blood draws.

Two blood samples will be collected at week 4 (pre-dose and 2-4 hours post dose), 1 blood sample at week 8 (collected at any time point post-dose within 24 hours) and 2 samples at week 12 (preferably 2 hours apart between 6 and 26 hours' post-dose). Exact timing of drug intake as well as relationship with food intake will be recorded for all blood draws. Subjects were will be asked to fast at least 6 hours prior to the intensive PK sampling visit and until 2 hours after dosing at site.

The intensive and sparse PK samples for ravidasvir will be combined and population PK parameters will be estimated using non-linear mixed effects regression.

12.2. Pharmacokinetic (PK) assessments of DAAs and Antiretroviral Drugs

12.2.1. Sparse PK samples collection in HCV/HIV coinfected patients for potential drugdrug interaction detection

The presence of concomitant Antiretroviral (ARV) medications will be coded as a binary variable (e.g. one variable per ARV drug) to estimate population PK parameters in the presence of the covariate i.e. to determine the fractional change due to the presence of the concomitant ARV drug(s).

Ravidasvir pharmacokinetics

The impact of co-administered antiretroviral drugs on ravidasvir PK parameters is investigated using a population pharmacokinetic approach (morning trough concentration and other available sparse samples). HCV mono-infected subjects (except those in the intensive PK study) and HIV/HCV co-infected patients receiving an NNRTIs (e.g. efavirenz, nevirapine) or PI (e.g. lopinavir/ritonavir or atazanavir/ritonavir) will have sparse PK sampling performed.

Antiretroviral Pharmacokinetics for HIV co-infected subjects

As part of the planned sparse PK sampling for ravidasvir, antiretroviral trough concentrations will be determined in the pre-dose sample collected at week 4. In addition, for all the subjects on ART a single plasma sample (e.g. trough or mid-dose) will also be collected at study entry prior to initiating the HCV treatment. The analysis of ARV trough concentrations will be descriptive and mean concentrations will be compared to historical ranges reported in adults and the recommended cut-off concentrations for virologic efficacy.

Potential for other drug-drug interactions

Stored blood samples may be used to assess blood levels of concomitant medications

13. Timing of assessments

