7.1. Schedule of visits and Study Assessments for non-cirrhotic patients

					On-Treatment Study Visits 12 weeks				R12)	4)	(ts ¹³
Evaluations / study procedures / study visit ¹	Eligibility (45 days to day -1)	Screening (30 days to day -1)	Day 1	Treatment Visit Wk. 1 +/- 3days	Treatment Visit wk. 4 +/- 7days	Treatment Visit wk. 8 +/- 7days	Treatment Visit W12 (End of Treatment or premature discontinuation) +/- 7days	Follow-up visit wk. 4 (SV (-1 day and +7 days)	Follow-up visit wk. 12 (SVI (-1 day and +28 days)	Follow-up wk.24 (SVR2 (-3 days and +28 days)	Long term Follow-up visit (-28 days and +28 days)
Information, counselling	X ²	Х									
Informed consent	Х										
Inclusion/exclusion criteria & demography		Х									
HCV, HBsAg, HIV	Х										
Medical history, full clinical examination ³ Height Weight		х									
Symptom directed assessment			Х	Х	Х	Х	Х	Х	Х	Х	Х
Concomitant medication review		Х	Х	Х	Х	Х	Х	Х	Х	Х	
AE review			Х	Х	Х	Х	Х	Х	Х	Х	Х
Vital signs		Х	Х	Х	Х	Х	Х	Х	Х		
Fibroscan ⁴		Х									X4
12 leads ECG		Х		Х			Х	X ¹⁴			
Hematology (full blood count)		Х	Х		Х	Х	Х	Х	Х		Х
Chemistry (alkaline phosphatase, serum albumin, direct/total bilirubin, ALT/ AST, serum creatinine)		х	х		х	х	х	х	х	X ¹²	Х
Fasting blood sugar (glucose)		Х									
Coagulation (PT, INR)		Х								Х	
Urinalysis		Х							Х		
Urine pregnancy tests ⁵		Х	Х	Х	Х	Х	Х	Х			
HCV RNA	Х			X ⁶	X ⁶	X ⁶	X ⁶	X ^{6a}	X ⁶	Х	Х
HIV RNA ⁷		Х							Х		
CD4 count ⁷		Х							Х		
HCV genotype		Х									Х
Stored Plasma and DBS ⁸	Х	Х	Х	Х	Х	Х	Х	Х	Х	Х	Х

				On-Treatment Study Visits 12 weeks					R12)	24))
Evaluations / study procedures / study visit ¹	Eligibility (45 days to day -1)	Screening (30 days to day -1)	Day 1	Treatment Visit Wk. 1 +/- 3days	Treatment Visit wk. 4 +/- 7days	Treatment Visit wk. 8 +/- 7days	Treatment Visit W12 (End of Treatment or premature discontinuation) +/- 7days	Follow-up visit wk. 4 (SV (-1 day and +7 days)	Follow-up visit wk. 12 (SV (-1 day and +28 days)	Follow-up wk.24 (SVR2 (-3 days and +28 days	Long term Follow-up vis (-28 days and +28 days
Resistance testing ⁹		Х									
PK Intensive Sampling (stage 1 only) ¹⁰					Х						
PK sparse sampling ¹¹					Х	Х	Х				
Predose ARV PK sample for subjects on ART			Х								
Hair sampling		Х					Х				
Adherence				Х	Х	Х	Х				
Study Drug Dispensing			Х		Х	Х					
PROQOL-HCV			Х			Х			X		

¹ Eligibility and screening can be done on the same day for already HCV diagnosed subjects

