9.1. Description of study drug

Sofosbuvir (SOF, Grateziano[®])

- 400 mg tablet orally once daily with food (in the morning) for 12 weeks for subjects with liver fibrosis Metavir stage F0-F3
- 400 mg tablet orally once daily with food (in the morning) for 24 weeks for subjects with Metavir stage F4, CTP Class A

Ravidasvir (RDV or PPI-668)

- 200 mg tablet orally once daily with food (in the morning) for 12 weeks for subjects with Metavir stage F0-F3
- 200 mg tablet orally once daily with food (in the morning) for 24 weeks for subjects with Metavir stage F4, CTP Class A

Sofosbuvir and Ravidasvir are to be taken orally with meals. Participants will be told to swallow tablets whole and not to chew or crush these tablets due the unpleasant taste of the active substance.

Missed dose: If it is within 18 hours of the normal time, participants should be instructed to take the tablet as soon as possible and then participants should take the next dose at the usual time. If it is after 18 hours of the normal time, the dose should be skipped and the next dose taken at the usual time. Participants should be instructed not to take a double dose.

In case patient vomits: The instructions below should be advised:

1. In the event of vomit occur, subject should contact site team immediately for further advice.

2. To re-dose SOF and RDV again if vomiting happened within 2 hours post dose. Else, take the next dose as usual.

3. If vomiting happened 2 times or more, within 2 hours post dose, no re-dosing is required. (maximum number of re-dosing that can be done is only 1 time, within the same dose interval). Adverse event has to be reported accordingly as per described in section 15.2.

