16.2.6. Pharmacokinetics

In stage 1, the pharmacokinetics of RDV will be evaluated using an intensive PK schedule for a small proportion of the subjects enrolled in healthcare institutions to establish the PK model and by population approach (sparse sampling) for the others. Twenty-five evaluable intensive PK evaluations will provide sufficient precision in the estimates of the PK parameters to use as initial estimates in the population model.

The population PK model (stage 1 and stage 2) built using these parameters allows, with a small number of samples per subject, collected at variable times between drug intake and sampling, to reestimate the pharmacokinetic parameters of the drugs as well as their variability in the population. This approach enables to explain the observed variability with various pertinent covariates such as possible antiretroviral co-treatment and patient's characteristics (e.g., BMI, sex, etc.).

Individual pharmacokinetic parameters are derived using Bayesian estimation from the population model. Association between individual exposures (i.e. trough concentration, area under the curve) and efficacy/tolerance endpoints are then investigated. The pharmaco-statistical analysis is performed using non-linear mixed effects modelling software (e.g. Monolix v4.2 or NONMEM v7.3) to calculate the pharmacokinetic parameters of all drugs as well as the covariates associated with inter-subject variability.

Given the reported drug-drug interactions between antiretrovirals and DAAs, RDV, NNRTI or PI morning troughs or mid dose concentrations are systematically measured in HIV/HCV co-infected subjects to verify that RDV as well as antiretrovirals are within exposure targets. Given the metabolic route of elimination of RDV, it is anticipated that drug-drug interactions, if any would be minimal.

Hair analysis has proved to be a suitable method to detect chronic or acute abuse of many drugs of abuse such as opiates, cocaine, amphetamines and many others. Hair samples are collected at baseline and at end of treatment for all subjects where possible. These samples will be used to assess drug use in subjects who fail to meet the primary study endpoint (SVR12).

Data management programs and all statistical analyses except pharmacokinetic modelling will be performed using Stata version 13 or higher.

17. Data Safety Monitoring Board

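### The week 4 antiretroviral trough is timed to the ravidasvir dose, so some values compared with efficacy cut-offs may be mid-dose

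*Protocol*

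**What the plan says.** Section 12.2.1 of the protocol takes the antiretroviral measurement from an existing draw. "As part of the planned sparse PK sampling for ravidasvir", it says, "antiretroviral trough concentrations will be determined in the pre-dose sample collected at week 4". That draw is defined in section 12.1.2, under ravidasvir: "Two blood samples will be collected at week 4 (pre-dose and 2-4 hours post dose". Ravidasvir is a morning drug; section 9.1 gives "200 mg tablet orally once daily with food (in the morning) for 12 weeks for subjects with Metavir stage F0-F3", and the 24-week regimen has the same morning timing.

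The analysis is described as one of antiretroviral trough concentrations. It is descriptive, and "mean concentrations will be compared to historical ranges reported in adults and the recommended cut-off concentrations for virologic efficacy".

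Other places describe the measurements differently. Section 16.2.6 says that "NNRTI or PI morning troughs or mid dose concentrations are systematically measured". For the sample before study treatment, section 12.2.1 says that "a single plasma sample (e.g. trough or mid-dose) will also be collected at study entry prior to initiating the HCV treatment", while the Day 1 row in the schedules in 7.1 and 7.2 reads "Predose ARV PK sample for subjects on ART".

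**The concern.** A trough is defined by the drug being measured. A draw taken just before ravidasvir is an antiretroviral trough only if the antiretroviral happens to be at the end of its own dosing interval. For a once-daily antiretroviral taken in the evening, a morning draw falls about 12 hours after the dose. For a morning antiretroviral swallowed before the visit, it falls soon after the dose. Section 12.2.1 nevertheless gives every week 4 pre-dose value the trough label and carries it into the comparison with cut-offs.

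Interaction with antiretrovirals is a named secondary objective (3.1.2), and 16.2.6 gives the purpose of these measurements as verifying that exposure is on target. Section 16.1.3 expects about 30% of the study population to be co-infected. If mid-dose values are read as troughs, a mean near or below a trough cut-off can look comfortable, and a fall in exposure during SOF-RDV treatment is harder to see.

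**Working it through.** The plan gives no sample size, precision target or numerical cut-off for the antiretroviral concentrations, so there is no figure to reproduce. The check is textual, followed by an illustration of size.

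**Step 1. What the week 4 draw is anchored to.**
- 12.1.2 and 12.2.1: it is the pre-dose draw of the ravidasvir sparse scheme.
- 9.1: ravidasvir is taken in the morning.
- 13.4: at PK visits subjects take the study treatment at the hospital; antiretrovirals are not mentioned.
- 5.2: antiretrovirals follow their package inserts, and no dosing time is fixed.

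No section asks for the antiretroviral to be held until the draw or ties the draw to its last dose. The post-dose time of the antiretroviral in this sample is therefore uncontrolled.

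**Step 2. How the values are labelled.**
- 12.2.1: the week 4 value is a trough, without qualification.
- 16.2.6: morning trough or mid-dose.

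The second is the accurate description of what the sampling yields. The first is the one attached to the cut-off comparison.

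**Step 3. Direction and size.** Assume steady state and log-linear decline, with dosing interval τ, sampling time t after the antiretroviral dose and half-life h. Then

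C(t) / C(trough) = 2^((τ − t)/h).

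The documents give no antiretroviral half-lives or dosing times; h = 12, 24 and 48 hours is an assumed range.

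| Assumed half-life | Once daily, drawn at 12 h of 24 h | Twice daily, drawn at 6 h of 12 h |
|---|---|---|
| 12 h | 2^(12/12) = 2.00 | 2^(6/12) = 1.41 |
| 24 h | 2^(12/24) = 1.41 | 2^(6/24) = 1.19 |
| 48 h | 2^(12/48) = 1.19 | 2^(6/48) = 1.09 |

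The ratio is above 1 for any t before the end of the interval on the declining phase, so the direction does not depend on the assumed half-life.

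**Step 4. Effect on a group mean.** If a share f of subjects is sampled mid-dose and the rest at trough, with the same underlying trough, the mean is inflated by 1 + f(r − 1), where r is the ratio above. With f = 0.5 and once-daily dosing:
- 12 h: 1 + 0.5 × 1.00 = 1.50
- 24 h: 1 + 0.5 × 0.41 = 1.21
- 48 h: 1 + 0.5 × 0.19 = 1.09 (rounded from 1.095)

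The documents give no value for f; 0.5 is only an example.

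**The case against.** The strongest reply has four parts.

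*Dose times are already collected.* Section 12.1.2 records the time of drug intake for all blood draws, and the antiretroviral assay uses one of those draws. This is a real partial safeguard, and it makes the repair smaller. But the sentence sits in the ravidasvir section and does not say whether it covers the antiretroviral, and the analysis in 12.2.1 does not use the time.

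*Sorting values before summarising belongs in the SAP.* In part it does. However, the trough label and the draw time are set in the protocol, and a SAP cannot recover a dose time that was never recorded.

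*The Day 1 wording is not a contradiction.* This stands. A reader might infer that the schedules' pre-dose label conflicts with the trough-or-mid-dose wording of 12.2.1. It does so only if pre-dose there means before the antiretroviral. Read as before the first study dose, it agrees with 12.2.1. The label is ambiguous and needs a definition.

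*The entry sample is not used to estimate an interaction.* This also stands. A reader might suppose that entry and week 4 values are to be subtracted, so that unequal post-dose times would bias an interaction estimate. Neither 12.2.1 nor 16.2.6 plans that contrast for antiretrovirals; the stated comparison is with historical ranges and cut-offs.

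**Conclusion.** The point holds in limited form. Section 12.2.1 labels as an antiretroviral trough a sample whose timing is set by another drug, and 16.2.6 concedes that some values may be mid-dose. Followed as written, mid-dose values can enter the cut-off comparison as troughs and bias it upward.

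The individual values would be overstated by about 1.2 to 2.0 times for once-daily dosing with a 12-hour draw, and by less for a group mean in which only some subjects are mid-dose. This rests on assumed half-lives of 48 to 12 hours, log-linear decline, an unknown share of subjects dosed at another time, and the cut-offs being trough cut-offs. The last is implied by the wording of 12.2.1 but not stated.

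Two stronger readings are not supported. The first is that the week 4 sample is never an antiretroviral trough; for a subject whose antiretroviral is due that morning and not yet taken, it is one. The second is that a halving of exposure would go unseen. That needs every subject on once-daily evening dosing and a 12-hour half-life unchanged by the interaction (0.5 × 2.00 = 1.00 of the original trough). At 24 and 48 hours the apparent value would be 0.5 × 1.41 = 0.71 and 0.5 × 1.19 = 0.59 (unrounded ratio), a visible fall.

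The analysis is descriptive and serves a secondary objective. SVR12 and the sample size are unaffected. It should be corrected because the error runs towards reassurance and the correction is cheap.

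**What to change.** 1. In 12.1.2 and 12.2.1, state that the drug-intake time recorded for each blood draw includes the last antiretroviral dose.
2. In 12.2.1, classify each antiretroviral value as trough or mid-dose by time since that dose, not by its position relative to ravidasvir.
3. Summarise the two classes separately, and compare each only with reference ranges or cut-offs that apply at that post-dose time.
4. Where no antiretroviral dose time exists for samples already drawn, report those values as of unknown timing and leave them out of the cut-off comparison.
5. Reconcile 7.1, 7.2, 12.2.1 and 16.2.6, and define what pre-dose means for the Day 1 antiretroviral sample.

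The cost is a clarified or added time entry on the PK form, some analysis wording, and fewer values in each comparison. No dosing time, visit or sample changes. Retiming the entry sample is not proposed: section 4.3 shows that stage 1 had finished by April 2018 and that stage 2 had been enrolling since January 2019, while this protocol version dates from March 2020. For the same reason, steps 2 and 3 can be applied to samples already collected only where the antiretroviral dose time is on record.

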3.1.2. Secondary Objectives

- To assess the efficacy of 12 weeks SOF-RDV in subjects with chronic HCV infection and no cirrhosis and 24 weeks SOF-RDV in subjects with compensated cirrhosis at 4 and 24 weeks after the end of study treatment.
- To assess the safety of 12 weeks SOF-RDV in subjects with chronic HCV infection and no cirrhosis, and 24 weeks SOF-RDV in subjects with compensated cirrhosis.
- To study the pharmacokinetics of SOF and RDV, evaluate potential drug-drug interactions with antiretrovirals and, as needed, interactions with concomitant prescribed or non-prescribed drugs.
- To describe the subjects' demographic, clinical and biological characteristics and their relationship with SVR12.
- To assess the subjects' quality of life before and after therapy.
- To evaluate the presence of viral resistance-associated variants (RAVs) to SOF-RDV at the time of failure or at first point after failure when viral load is sufficient to get a positive result in patients with virological failure and their persistence until 1 year after treatment cessation or the initiation of an alternative HCV therapy.

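### The antiretroviral level analysis names only external comparators, so it can show whether exposure is adequate but not whether SOF-RDV changed it

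*Protocol*

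**What the plan says.** Section 3.1.2 lists as a secondary objective: "To study the pharmacokinetics of SOF and RDV, evaluate potential drug-drug interactions with antiretrovirals and, as needed, interactions with concomitant prescribed or non-prescribed drugs".

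Section 12.2.1 plans two ARV measurements in subjects on ART. Before HCV treatment, "for all the subjects on ART a single plasma sample (e.g. trough or mid-dose) will also be collected at study entry". On treatment, "antiretroviral trough concentrations will be determined in the pre-dose sample collected at week 4". On the analysis it states: "The analysis of ARV trough concentrations will be descriptive and mean concentrations will be compared to historical ranges reported in adults". The same sentence goes on to name efficacy cut-offs as a second comparator. Section 16.2.6 gives the purpose of measuring these concentrations as "to verify that RDV as well as antiretrovirals are within exposure targets".

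The schedules in sections 7.1 and 7.2 list the entry sample once, on Day 1, as "Predose ARV PK sample for subjects on ART". Section 5.2 requires an unchanged ARV regimen for at least 8 weeks before screening, expected to continue through the study.

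**The concern.** A historical range or an efficacy cut-off shows whether a group's exposure is acceptable. It does not show whether exposure moved after SOF-RDV was added, because the historical subjects differ from these in population, assay and adherence. A real fall or rise can therefore stay inside the range and be reported as unremarkable.

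The design already holds the material for a better contrast: one sample before and one during SOF-RDV, in the same person on the same regimen. The protocol uses an in-trial contrast for the opposite direction, where each ARV is a covariate in the ravidasvir population model. For the effect of study drug on ARVs it names only outside references.

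At stake is how well the trial can inform one half of the interaction objective, using samples it already plans to take.

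**Working it through.** **Plan's own figures.** The protocol gives no figure for the ARV comparison. Section 16.1.4 says the sample size for drug-interaction assessment will be met, but its only calculation is for ravidasvir AUC: (1.96 × 0.458 / 0.20)² = 20.1, so 21 subjects, or 23 with the t quantile. After 5-10% non-evaluable this becomes 23-26, which agrees with the stated 25. It does not bear on the ARV question.

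**Subjects available.** Section 16.1.3 expects about 30% co-infected: 0.30 × 600 = 180. Section 16.1.4 says about one third: 600 / 3 = 200. Both counts include co-infected subjects not on cART, who are eligible under section 5.2 and give no ARV sample. The rest divide among several NNRTI and PI regimens, so the number per ARV is unknown and clearly smaller.

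**Precision of a paired ratio.** Assumption: within-subject SD of log concentration 0.3-0.5 per occasion (not in the documents). The 90% CI factor is exp(t(0.95, n−1) × SD × √2 / √n).

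| n per ARV | SD 0.3 | SD 0.4 | SD 0.5 |
|---|---|---|---|
| 20 | 1.18 | 1.24 | 1.31 |
| 60 | 1.10 | 1.13 | 1.17 |

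For example, at n=20 and SD 0.5: 1.729 × 0.5 × 1.414 / 4.472 = 0.273, and exp(0.273) = 1.31.

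For an observed 25% fall (ratio 0.75), the upper limit at n=60 is at most 0.75 × 1.17 = 0.88, clearly below 1. At n=20 and SD 0.5 it is 0.75 × 1.31 = 0.98, barely below 1. An observed 30% rise in that case has a lower limit of 1.30 / 1.31 = 0.99, so it would not be distinguished from no change.

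**The same change against a historical range.** Assumption: between-subject CV 40-80%, so the log SD √ln(1 + CV²) is 0.385-0.703. A 30% fall in every subject is −ln(0.70) = 0.357 on the log scale, or 0.357 / 0.385 = 0.93 SD down to 0.357 / 0.703 = 0.51 SD. The lower end of a historical 95% range is exp(−1.96 × SD) = 0.47 to 0.25 of the median. If the trial's subjects start near the historical median, a mean at 0.70 stays inside it.

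**Is the gain only precision?** At n=50, with between-subject CV 40-80% and within-subject CV half of that, the 95% CI factor is 1.08-1.17 for the paired ratio and 1.13-1.26 for the week-4 mean alone. If both CVs are 60%, both factors are 1.25 and pairing gains no precision. It still removes the difference between the trial population and the historical one.

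**Timing.** The schedules call the Day 1 sample pre-dose; section 12.2.1 allows a trough or a mid-dose level at entry; section 16.2.6 also allows either. The week-4 sample is pre-dose within the ravidasvir sampling scheme. No section says which drug's dose is the reference at Day 1.

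**The case against.** The strongest reply is that the protocol nowhere says the entry sample goes unused. A descriptive analysis does not rule out showing change, and an SAP or PK plan, not shown here, could add a paired summary. Section 16.2.4 even specifies the Wilcoxon signed-rank test for changes from baseline, though under efficacy. This stands in part: a reader might infer that the trial discards its own control, but the text supports only that the comparators it names do not address change. Because the protocol names them rather than leaving the choice open, the sentence is still worth changing.

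Second, section 16.2.6 frames the purpose as adequacy of exposure, for which cut-offs are a natural reference. That stands, and is the reason to keep them. It does not cover the interaction objective.

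Third, a reader might infer that the entry and week-4 samples are mismatched in time. That is not established: pre-dose in the schedule may mean before the first SOF-RDV dose, while trough or mid-dose may refer to the ARV dose. The wording needs reconciling; a mismatch is only possible.

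Fourth, a paired ratio does not prove that SOF-RDV caused a change. It rests on one sample per occasion without a control group, and adherence or dose timing may shift between visits. That stands.

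**Conclusion.** The point holds as a modest, inexpensive improvement. As written, the ARV analysis can say whether exposure is adequate but cannot estimate the change after SOF-RDV, although the samples for such an estimate are planned and the regimen is meant to be stable.

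The size of the benefit rests on assumed variability and on an unknown number of subjects per ARV. A change of about 25% would be clear with 60 subjects on one drug under the assumptions above, and may be unclear with 20. A reader might take the 180 co-infected subjects as the number available per drug; the documents do not support that, nor do they establish that any single ARV reaches 60.

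The effect is confined to the influence of study drug on ARVs, a descriptive part of a secondary PK objective.

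**What to change.** In section 12.2.1, for each ARV drug, report the within-subject week-4/entry geometric mean ratio with 90% CI for subjects whose two samples fall at a comparable time after the ARV dose. Where the times differ and ARV intake time is recorded, use a mixed model for log concentration with time since ARV dose. Section 12.1.2 records drug intake times for the sparse draws but does not say that this covers ARVs. Keep the efficacy cut-off comparison alongside, for adequacy of exposure, and describe the ratio as an uncontrolled before-after estimate.

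Reconcile the sample descriptions in sections 7.1, 7.2, 12.2.1 and 16.2.6, and state which drug's dose is the reference.

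Cost: analysis wording and a little extra work, with no new visit or sample. Pairs with unmatched times need the model or drop out. Stage 1 follow-up to week 24 ended in April 2018 and stage 2 has enrolled since January 2019, so aligned timing can help only subjects not yet sampled; for the others only the analysis change is available.
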